9.4.8 Reader Training

All readers will require significant training and it is important for the pilot and for the main trial that readers are fully trained before the commencement of recruitment. The non-radiologist (Reader 1) will be required to undergo training on 100 CTs which will comprise a mix of validated cases from the NELSON study (details below). The radiologist (Reader 2) would require at least 30 cases and both readers will receive application training on the Siemens LungCare and UKLS database software.

The training set CTs, derived from NELSON studies, will consist of screening examinations that demonstrate:

- 1) Imaging findings ranging from normal to overtly abnormal, with the inclusion of focal opacities (including a range of non-solid and other “difficult” lesions) commonly observed in the course of CT screening

- 2) Examples from which definitions of what constitutes a lung nodule, and nodule characteristics, such as density, margin and volume, can be imparted
- 3) Cases with deviations from the technical parameters specified by the protocol, including examples of important suboptimal image quality for whatever reason, e.g. motion, beam hardening, under-inflation of the lungs, etc.

Readers will be tested on a different batch of test cases. Reader 1 will be required to read 50 nodules in test conditions and readers 2 and 3 will be required to read 25 nodules in test conditions. A concordance rate of 80% compared to the NELSON standard will be required and all central and local readers will need to achieve this "pass standard" prior to being signed off to read within the trial.

9.4.9 Quality Assurance

As above, all readers prior to reporting will have to undergo training and pass the competency test on validated NELSON cases. Radiologists involved with the reading of CTs (central or local sites) must be registered with the General Medical Council and accredited by the Royal College of Radiologists UK (or equivalent). Radiologists should have a specialist interest in thoracic imaging and have been involved with the supervision and/or performance, review and interpretation of at least 300 chest CT examinations in the previous three years.

9.4.10 Pilot Phase

During the pilot there will be regular feedback of performance to the local centres in comparison to the consensus view. Detailed analysis of individual scores will be made. Development of audit scoring system to grade level of discrepancy will be made:

- 5 Complete agreement
- 4 Trivial difference in read – e.g. difference in description of nodule but no change in outcome
- 3 Minor disagreement – unlikely to be of any clinical significance
- 2 Moderate disagreement – could be of clinical significance
- 1 Major error in interpretation - failure to report a significant nodule (e.g. 8mm diameter nodule) with change in outcome

As part of the pilot the development of reference range for discrepancy to trigger a review of a reader/centre will be formulated.

[figure not shown]
9.4.11 Main Phase

Formal audit will be taken continuously with grading of adequacy of scan and reader concordance. In addition to initial training of readers, annual site visits, central quarterly monitoring meetings and an annual investigators' meeting will be organised.

10 UKLS Care Pathway

Figure 2: UKLS Care Pathway

Figure 1: UKLS Nodule Care Pathway Management Protocol

11 MDT Assessment

The Respiratory Physician will collate all of the clinical information for presentation to the Multidisciplinary Team (MDT). The MDT will determine the best management options for the study participant (who now becomes a patient) by considering the risks and benefits of each option. Risk will be determined by the fitness assessment and the risk of the procedure to the patient. Benefit will relate to the probability that the lesion identified by screening is malignant. The MDT will need to assess fitness for surgical or other radical procedures and the risk of malignancy. The management options (with preferred option) would then be discussed with the patient and patient's preferred option adopted. The MDT will assess fitness from the clinical history and objective testing. The former will include identification of co-morbidities and the latter will be tailored to the individual to include tests relating to co-morbidity (such as cardiac exercise testing for ischaemic heart disease) and those assessing respiratory fitness such as lung function testing and quantitative ventilation/perfusion scanning. The risk that the lesion is malignant will be higher for larger nodules, or those that have shown growth. In these circumstances, or where the CT has shown obvious cancer, the normal work-up employed by the MDT will be adopted. This will usually involve a Positron Emission Tomography - Computed Tomography (PET-CT) scan if the patient is thought to be suitable for radical treatment, fitness assessment as above and a biopsy or immediate resection. For smaller nodules (<1.5cm) the MDT would be helped considerably by being provided with an estimated probability that the nodule is malignant. This is so the MDT can balance the potential risk and benefits of the options of biopsy, surgery or a period of monitoring for signs of malignancy (growth on serial CT). Thus UKLS will provide an estimate of malignancy for smaller nodules.

11.1 The UKLS Care Pathways

Diagnostic workup and treatment algorithms are already available within NHS practice. However, the detail of the UKLS Care Pathways has been amended to cater for the management of nodules of differing sizes. The clinical care pathways comply with current standards and where possible existing clinical protocols are employed such as those recommended by National Institute for Health and Clinical Excellence (NICE). The pilot study will employ the agreed pathways, as detailed in Figure 2: UKLS Care Pathway and Figure 3: NICE Lung Cancer Investigation Care Pathway. These pathways will be modified if deemed necessary by the Steering Committee, and the full study will add to the subjects enrolled in the pilot.

The Care Pathways are summarised in Figure 2: UKLS Care Pathway for individuals who participate in the UKLS Trial. The algorithms are presented according to the findings of the CT. If there are no findings then there is no further active follow-up of the individual.

It is anticipated that some subjects will have significant other diseases and they will be referred back to their GP.

There are significant differences in the way smaller nodules, larger nodules and more obvious lung cancers are managed, thus this forms the major part of the UKLS Care Pathway. The methodology by which the nodules are handled is based on the NELSON protocol, which has been tried and tested in 10,000 individuals [21]. These patients will be discussed at the Trial Centres' MDT meetings and their treatment

[figure not shown]
planning will be based on the Care Pathway flow diagram outlined in Figure 2, which is based on NICE guidelines.

Patients will need to be kept informed of their position in the management pathways and given opportunities to have their concerns addressed. The pathways described are according to accepted standards. Appropriately trained personnel will discuss all scan results with subjects.

The follow-up of small nodules and action taken will depend on a discussion of the risks and benefits of three options with the subject – observe for a prescribed period, transthoracic needle biopsy or excision. There will be a recommended approach according to size of nodule and rate of growth, but the subjects together with their doctor will make an informed decision about the approach taken.

In the unlikely eventuality that a participant will require care that falls outside of the UKLS Care Pathway due to unforeseen clinical presentation, the time interval for the repeat CT scan may be reassessed and amended accordingly. This may also effect the decision of *when* to refer the participant to the Multi-Disciplinary Team. On these rare occasions, the decision to work outside of the UKLS care pathway must be taken by the first **and** second read radiologist and documented on the UKLS database.

Figure 3: Summarised NICE Lung Cancer Investigation care pathway

12 Pathological Investigations

The UKLS Pathology protocol provides recommendations for uniform handling of specimens obtained during a CT-screening trial. The primary aim is to provide a pathologic diagnosis to facilitate the management of trial patients who have lung (or associated tissue) lesions biopsied and, in some cases, lung lesions subsequently resected. A secondary aim is, where possible, to provide appropriate tissue for biomarker and other translational research as part of additional studies complimenting the screening project. The pathology/biomarker protocol is intended for the handling of these specimens in a standardised fashion, which is based on current best practice and used by the majority of thoracic pathologists, as outlined in The Royal College of Pathologists (RCPATH) guidelines for handling lung cancer resection specimens. The UKLS pathology protocol also includes freezing of tissue samples where available, for translational research. The UKLS pathology protocol is detailed in Appendix J: Pathology Protocol.

The local pathologist is the nominated specialist pulmonary pathologist at the surgical centre where the patient is treated. This pathologist is responsible for the primary diagnosis and reporting of the case, this is the diagnosis on which the patients' subsequent management will be decided. This diagnosis will also be used for evaluation of the 'disease-specific mortality' endpoint within the trial.

Pathological specimens, particularly tumour tissue collected from consented participants who have been referred to the MDT will be transported to the University of Liverpool Cancer Research Centre, [name], Liverpool where they will be stored securely in line with local policy and SOPs.

13 Surgical Protocols

The Surgical Review group have decided that the NICE guidelines, published in February 2005, provide an entirely appropriate protocol for the selection of patients for lung cancer surgery which derive from the UKLS trial. These patients will be managed through the MDT according the UKLS Pathway.
(<http://www.nice.org.uk/nicemedia/pdf/cg024fullguideline.pdf>)

14 Assessments and Procedures

14.1 Schedule for Follow-up

Once a participant has been randomised onto the UKLS trial they will be followed up for a period of 10 years. Follow-up information on all participants will be collected indirectly through either Cancer Registry or via The Office of National Statistics (ONS). A subset of participants will be contacted to complete the Psychosocial and Health Economics questionnaires.

14.2 Follow up

All participants randomised onto the UKLS trial will be registered with either the National Health Service Central Register for England and Wales (ONS) or the Cancer Registry. The computerised randomisation for each subject at the registry will be tagged for prompt notification to the study directors in the event of new cases of cancer and deaths from cancer in the study population. The registry will also notify the LCTU of individual subjects who do not appear on the register so that further information required to trace their entry, can be obtained or alternative methods of follow up can be employed.

14.3 Psychosocial and Health Economics

A subset of participants will be asked to take part in the Psychosocial evaluation and Health Economics section of the study. Equal numbers from each study arm will be asked to take part. These participants will be selected at random from the original 4,200 randomised. A brief baseline psychosocial questionnaire will be completed at the clinic recruitment session. Follow-up psychosocial questionnaires will be sent directly to all participants at 1 month post randomisation (i.e. in the screening group, approx. 2 weeks after CT scan results are received – both baseline and follow up scans). These data will be scanned and uploaded onto the UKLS database and analysed.

One objective of the psychosocial evaluation is to assess potential participation bias to the UKLS pilot trial and highlight potential hard to reach groups within this cohort. Analyses will compare the following groups on age, gender and socio-economic status: 1) non-responders, 2) those who complete the non-participation questionnaire (negative responders) and 3) those who complete the UKLS 1st questionnaire (positive responders).

In order to complete these analyses the mail sorting organisation working with UKLS (RADAR) will provide the UKLS study team with data on age and gender of non-responders to the initial approach letter. RADAR will compute the Index of Multiple Deprivation (IMD) scores (a measure of socio-economic deprivation) for all approached individuals using their postcodes and release the IMD information to the UKLS team. The data sent to UKLS is non-identifiable (age, gender and IMD score of each individual).

We have contacted the National Information Governance Board for Health and Social Care (NIGB) who have informed us that we do not need to submit an amendment to them because the proposed analyses are compatible with the purpose of the original NIGB application and there is no flow of patient identifiable information as the UKLS team receive anonymised data from RADAR. Evidence of this can be found within the UKLS Trial Master File.

The Health Economics questionnaire data will be analysed at Nottingham University under the direction of Professor [name].

Psychosocial analysis plan

The primary psychosocial outcome is cancer worry measured using the 6-item revised Cancer Worry Scale [22, 23] adapted for lung cancer. It is hypothesised that trial participants will report increased short-term cancer worry compared to controls, and that those recalled for further tests will report increased cancer worry in the short- and longer-term.

Preliminary analyses

Attrition analyses will first be conducted to examine the sociodemographic (e.g. gender, age, SES, ethnicity) and clinical (e.g. smoking duration, personal and/or familial experience) factors associated with questionnaire non-response at each stage of the psychosocial assessment, using chi-square and independent t-tests as appropriate. Equivalence of trial/control groups in sociodemographic, clinical, and baseline psychological measures will be examined using chi-square and independent t-tests as appropriate. Descriptive statistics will then be used to characterise study participants in terms of sociodemographic and clinical background factors, and to examine the proportion of the sample reporting clinical levels of HADS anxiety/depression and high levels of cancer-specific worry.

Primary analyses

Prior to the main analysis, multivariate assumptions of normality and linearity will be tested. If the outcome data are reasonably normally distributed, repeated measures analysis of covariance will be used to assess any main effects of trial condition on changes in psychological responses (i.e., cancer worry, anxiety, depression, and decision satisfaction) from baseline to four week follow-up, controlling for potential confounding variables such as gender and baseline distress. If the outcome data are not normally distributed, scores may be transformed to produce a more normal distribution using logarithm transformations.

Secondary analyses

Regression analyses will be carried out to examine the predictors of cancer worry, anxiety, depression, decision satisfaction and screening intention at four weeks. Potential predictors include trial condition/CT screening result, gender, age, SES, ethnicity, smoking duration, personal and/or familial experience of lung cancer, lung screening history, screening expectation, and baseline distress measures.

The CARA Model [24] provides a suitable theoretical framework for understanding the role of expectations in predicting psychological responses to screening within the intervention arm. This model suggests that unexpected bad news (i.e. an abnormal CT scan result) will evoke high cognitive effort, a tendency to downplay the accuracy of the information, and a negative emotional response to CT lung screening. Respondents in the intervention arm will be divided according to whether, at pre-screening baseline, they expected to receive a normal/clear result or an abnormal result. A 2 x 2 ANOVA will be used to compare differences in responses to screening results (perceived threat and perceived accuracy) according to consistency between screening expectation (positive vs. negative) and actual result (normal vs. abnormal).

Sub-studies

Participants will be asked to provide up to 24mls of blood, two buccal swabs, nasal swabs and sputum samples as part of their recruitment clinic appointment (subject to appropriate consent as detailed in section 17.3). The samples will be transported to the UKLS biobank held at the University of Liverpool LECMC GCLP facilities for storage.

24 mls of blood will also be collected from participants referred to the Multi-Disciplinary team prior to surgery or investigation as well as at subsequent out-patient follow up visits. Blood collected from participants referred to the Multi-Disciplinary Team will be transported to the University of Liverpool Cancer Research Centre, [name], Liverpool.

Participants will also be given a sputum collection kit to take home. They will be asked to deposit three morning sputum samples and post the sample back to the UKLS biobank in postage paid Royal Mail Safe Boxes.

15 Statistical Considerations

15.1 Introduction

This study has been designed to have power to detect a significant realistic and clinically worthwhile effect of the intervention. We are particularly interested in the effect in a higher risk population than NELSON, as we feel that if there were a service screening programme in the future, it would probably be neither ethical nor feasible to offer the service to low or medium risk individuals. However, the effect of the screening as estimated in the two trials can be combined in the fullness of time, which gives a safety net for statistical power in case the intervention has a lesser effect than anticipated. The Trial design for UKLS will use the Wald one screen design detailed in section 6.3 UKLS Trial Design.

The reasons for the one screen design are based on:

- It is the most economical approach in terms of the number of CT screening examinations needed for a fully powered trial (see section 15.2 below)
- It will provide early data on rates of cancers in the years following a screen, to inform 'interval' for subsequent screens in a National Screening Programme
- It will produce mortality results in a similar time frame as the other major international multi-centre screening trials, and allow us to synchronise our data with the multi-centre groups for analysis
- The single screen design does not have the problem of long term compliance
- Other screening trials have used this design, including the UK Flexisig Trial, the UK Aortic Aneurysm Screening Trial and the Singapore Breast Screening Trial.

15.2 Sample Size

The sample size/power calculations had the aim of determining a screening schedule which would optimise when and with what study size a significant result is likely in UKLS, with respect to the comparison of lung cancer mortality in the intervention and control group. The question of particular interest is whether a study offering only a single screen to the study group, or one offering multiple screens, is likely to be more efficacious in terms of:

- (1) how soon a significant result can be expected; and
- (2) resources expended on screening

Without actually carrying out the full trial, the timing and magnitude of the effect on mortality, if any, cannot be known for certain. We can, however, arrive at estimates using published data on the following quantities:

- The incidence of lung cancer in the target population
- Uptake of screening
- The mean sojourn time (MST) of asymptomatic lung cancer (i.e. the duration of the window of opportunity for asymptomatic detection) and its inverse, the rate of progression from asymptomatic to symptomatic disease
- Sensitivity of the screening test, CT scanning
- Survival of asymptomatic lung cancer cases, possibly taking into account length bias/over diagnosis

- Survival of symptomatic lung cancer cases

Single screen design

Although we shall use estimates of instantaneous rates of transition (e.g. from asymptomatic to symptomatic disease, from alive to dead), we shall convert these to discrete time probabilities, to obtain simple deterministic models. Let:

I = Annual incidence rate of lung cancer in target population

λ_1 = Instantaneous rate of transition from asymptomatic to symptomatic disease (=1/MST)

λ_2 = Instantaneous death rate from lung cancer of asymptomatic cases

λ_3 = Instantaneous death rate from lung cancer of symptomatic cases

S = sensitivity of the screening test

We assume a uniform annual incidence and exponential rates of progression to symptomatic disease and death [25]. We first demonstrate how to estimate the cumulative death rates in intervention and control groups for the simple case of a single screen study. In the intervention group, at time point 0, the expected rate of detection of asymptomatic lung cancers in those attending for screening is:

$$P = \frac{IS}{\lambda_1}$$

as shown by Paci and Duffy [26]. Launoy and colleagues [27] have shown that in a programme with a screening interval of r years, the expected proportion of tumours in those attending which are screen-detected is:

$$PS = \frac{S(1 - e^{-\lambda_1 r})}{\lambda_1 r(1 - (1 - S)e^{-\lambda_1 r})}$$

It follows that the cumulative rate of symptomatic cancers arising in the r years after a screen years will be:

$$I_r = I(1 - PS)$$

The number of symptomatic cancers arising in the first year after a screen is I_1 . The number arising in the r th year ($r=2,3,4\dots$) after a screen is $I_r - I_{r-1}$. In the control group, and in those who elect not to be screened in the study group, the annual rate of symptomatic cancers is I .

The cumulative rate of lung cancer death by the end of year r from asymptomatic tumours diagnosed in the intervention group at the single screen at the beginning of the study is estimated as:

$$D_1 = P(1 - e^{-\lambda_2 r})$$

The corresponding cumulative death rate in the control group is estimated as:

$$D_0 = I \sum_{i=1}^r (1 - e^{-\lambda_3(i-0.5)})$$

This uses the approximation of time of diagnosis as the midpoint of the relevant year. For the symptomatic tumours arising after the screen in the intervention group, the expected cumulative death rate is:

$$D_0 = \sum_{i=1}^r (I_j - I_{j-1})(1 - e^{-\lambda_3(r-j+0.5)})$$

where we define I_0 as 0.

We now require estimates of the various quantities. Let us first suppose that we shall be selecting a fairly high risk group for the trial, with a minimum annual incidence of five per thousand and an average annual incidence of seven per thousand. Thus $I=0.007$. From a recently published overview, we have estimates $\lambda_1=0.49$ and $S=0.96$ [28]. Five-year survival from lung cancer in the UK has been reported as 6% [29], corresponding to $\lambda_3=0.56$. Henschke et al [30] report 85% 10-year survival of 412 stage I screen-detected cases. Assuming that the 72 screen-detected cases in their series with stage II or worse disease had zero ten-year survival, this would give an overall ten-year survival of 72%. Hypothesising further that this is artificially high as a result of length bias/overdiagnosis, we assume a ten-year survival of 50%. Thus we are estimating the effect of screening on mortality from the 'real', life-threatening tumours, rather than inflating the incidence of the intervention group and retaining the very high survival rate. This gives $\lambda_2=0.07$. We assume an uptake rate of 80%, which seems high but reflects the motivated nature of this group, already demonstrated by their positive response at two stages of approach.

WALD Single Screen Design

The resulting estimates of cumulative lung cancer mortality are shown in Table 1, adjusted for the 80% compliance. The Table also shows the relative risks of lung cancer death, and the numbers required per group (assuming equal group size) for 90% power to detect the difference as significant, with 2-sided testing at 5% level. The optimum time of analysis would be at the end of three years, and 16,000 subjects per group would be required (32,000 in all). The time to the result, taking into account the recruitment period, would be more likely to be around five years.

Year	Cumulative lung cancer mortality (study)	Cumulative lung cancer mortality (control)	RR (intervention vs control)	Number required per group
1	1.0	1.2	0.83	368,000
2	3.1	4.0	0.78	63,000
3	5.3	7.8	0.69	16,000
4	9.2	12.1	0.76	20,000
5	13.4	16.7	0.80	21,000
6	17.9	21.4	0.83	24,000

Annual screening for three years

The calculations of the expected incidence of screen-detected and symptomatic tumours in the intervention group are similar to those for the single screen design, although now there is a mix of screen-detected and symptomatic tumours in the first three years. The cumulative mortality, relative risks and numbers required for 90% power are shown in Table 2.

The optimum power is achieved at 5 years, with 7,000 per arm. One might expect to add one year to this for recruitment.

Year	Cumulative lung cancer mortality (study)	Cumulative lung cancer mortality (control)	RR (intervention vs control)	Number required per group
1	1.0	1.2	0.83	368,000
2	2.8	4.0	0.69	35,000
3	5.0	7.8	0.65	13,000
4	7.8	12.1	0.64	8,000
5	11.2	16.7	0.67	7,000
6	15.2	21.4	0.71	7,200

Allowing for the 80% compliance rate, the single screen arm would incur screening costs for 12,800 CT scans (80% of 16,000). The 3-screen study would incur 16,800 scans (80% of 3 x 7000). Thus it would seem that the single-screen design, based on an idea by [name], would be more economical and would return an answer to the basic question earlier. We therefore propose a single screen in the study group vs usual care in the control group, with 16,000 subjects per group. We are aware that this design is not entirely conventional and that in a service screening programme, repeated screening would apply. Also, it has implications for analysis and interpretation (see below). However, in addition to its cost-effectiveness as a design, it has a number of other benefits.

The modelling has been carried out varying the parameters, and the single screen design has generally been more cost-effective. Also, the estimation of mortality from the rather simple semi-deterministic model above has been checked against a full stochastic model and results were in agreement.

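### Section 15.2 states an annual incidence of 7 per 1,000, but the control mortality column of Tables 1 and 2 is computed at 5 per 1,000, while the group sizes fit 7 per 1,000

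*Protocol*

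**What the plan says.** Protocol section 15.2 describes the target population as one "with a minimum annual incidence of five per thousand and an average annual incidence of seven per thousand", and sets I = 0.007. The other inputs are λ1 = 0.49, S = 0.96, λ2 = 0.07, λ3 = 0.56 and 80% uptake. Control mortality has its own formula, introduced by "The corresponding cumulative death rate in the control group is estimated as".

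The section then presents the output as following from those inputs: "The resulting estimates of cumulative lung cancer mortality are shown in Table 1, adjusted for the 80% compliance". For the three-screen design it says: "The cumulative mortality, relative risks and numbers required for 90% power are shown in Table 2". Both tables carry the same control column. Sizes are for 90% power with a two-sided 5% test and equal groups. Table 1 at year 3 gives 5.3 (study) and 7.8 (control), a relative risk of 0.69 and 16,000 per group. That row is the basis for 32,000 participants in the main trial. Nothing in the section says that the tables use the minimum incidence rather than the average.

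**The concern.** By the protocol's formula the control column depends only on I and λ3. Uptake, sensitivity, sojourn time and the survival of screen-detected cases do not enter, so no modelling choice for the screened arm can explain a control value that does not match the stated inputs. The printed values are about five-sevenths of what I = 0.007 produces.

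The printed year-3 rates and the 16,000 stand in the same table row, and the main trial's size is taken from that row. If the two rest on different incidences, 16,000 per group does not have the stated 90% power at the rates printed beside it. Anyone who works out expected deaths from the table would also get a number about 29% below what the stated incidence implies.

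**Working it through.** **1. Control column.** Formula: D0 = I × Σ(i=1..r) (1 − exp(−λ3(i − 0.5))), with λ3 = 0.56. Dividing each printed value by the sum gives the implied I.

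| Year | Sum | Printed (per 1,000) | Implied I | At I = 0.005 | At I = 0.007 |
|---|---|---|---|---|---|
| 1 | 0.2442 | 1.2 | 0.00491 | 1.22 | 1.71 |
| 2 | 0.8125 | 4.0 | 0.00492 | 4.06 | 5.69 |
| 3 | 1.5659 | 7.8 | 0.00498 | 7.83 | 10.96 |
| 4 | 2.4251 | 12.1 | 0.00499 | 12.13 | 16.98 |
| 5 | 3.3446 | 16.7 | 0.00499 | 16.72 | 23.41 |
| 6 | 4.2986 | 21.4 | 0.00498 | 21.49 | 30.09 |

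I = 0.005 reproduces every printed value to within 0.1. A free fit of both parameters to the column returns I = 0.00499 and λ3 = 0.557. With I held at 0.007, the best λ3 (0.29) gives 0.95, 3.43, 7.06, 11.54, 16.65, 22.25, which does not fit.

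**2. Group sizes.** Two proportions, pooled variance under the null, two-sided 5%, 90% power:

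n = [1.96√(2p̄(1−p̄)) + 1.2816√(p1(1−p1) + p2(1−p2))]² / (p2 − p1)²

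Table 1, year 3, printed rates: p1 = 0.0053, p2 = 0.0078, p̄ = 0.00655. The bracket is 0.2236 + 0.1462 = 0.3698, and 0.3698² / 0.0025² gives n ≈ 21,900 (21,878 unrounded). Rounding of the printed rates moves this only between 20,228 and 23,737.

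Multiplying both rates by 0.007/0.005 = 1.4 keeps the relative risk and gives 7.42 vs 10.92 per 1,000. Then n = 15,585 (16,152 with continuity correction; 15,928 on the log relative risk scale).

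| Year | Table 1 stated | From printed rates | From rates × 1.4 | Table 2 stated | From printed rates | From rates × 1.4 |
|---|---|---|---|---|---|---|
| 2 | 63,000 | 91,774 | 65,459 | 35,000 | 49,448 | 35,271 |
| 3 | 16,000 | 21,878 | 15,585 | 13,000 | 17,044 | 12,142 |
| 4 | 20,000 | 26,327 | 18,724 | 8,000 | 11,195 | 7,964 |
| 5 | 21,000 | 28,604 | 20,306 | 7,000 | 9,554 | 6,785 |
| 6 | 24,000 | 33,046 | 23,414 | 7,200 | 9,820 | 6,961 |

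Rounding does not close the gap to the printed-rate sizes in any of these years. The × 1.4 sizes agree with the stated ones within rounding of the rates, or with a continuity-corrected or log relative risk form. Year 1 is too sensitive to rounding to be informative.

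**3. Power of 16,000 per group at year 3.** Printed rates: Φ[(0.0025√16,000 − 0.2236)/0.1141] = Φ(0.81) ≈ 79%. Rates × 1.4: 90.7%.

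**4. Derived control deaths by year 3 in 16,000.** 16,000 × 0.0078 ≈ 125; at I = 0.007, 16,000 × 0.01092 ≈ 175.

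**5. A separate departure in Table 1's study column.** The printed I_r = I(1 − PS) lacks the factor r that a cumulative rate needs; I use I·r·(1 − PS). At year 3, per unit of I:

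- Deaths from screen-detected cases: (0.96/0.49)(1 − exp(−0.21)) = 0.371.
- Deaths from later symptomatic cases: I_r = 0.222, 0.758, 1.477 for r = 1, 2, 3, giving 0.647.
- With 80% uptake: 0.8 × (0.371 + 0.647) + 0.2 × 1.566 = 1.128.

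That is 5.64 per 1,000 at I = 0.005, against a printed 5.3. At year 2 the model gives 2.86 against 3.1. The other years agree to within about 0.2.

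**The case against.** The strongest defence is that the size itself is sound: at 90% power the group-size columns follow the stated I = 0.007, so only the displayed mortality rates are wrong. Much of this stands. It means one should not infer that 16,000 was sized for a 5 per 1,000 population. But the table still offers 5.3 vs 7.8 as the rates that 16,000 detects with 90% power, and it does not.

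A second reading keeps the printed rates and supposes 80% power was used. That gives 16,343, 19,666, 21,367 and 24,685 for Table 1 years 3 to 6, which is also close. The sizes alone therefore cannot settle the cause. This reading contradicts the stated 90%, however, fits Table 2 at years 2 and 4 less well, and leaves the control column at odds with I = 0.007.

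A reader might also infer that 16,000 falls short of 90% at either incidence because of this mismatch. The documents do not support that. Correcting the incidence alone, with the printed relative risk kept, gives about 91%. A shortfall at both incidences appears only if the study column is also recomputed from the model with the factor r supplied (step 5).

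Finally, the protocol prints rates, not planned event counts, and section 15.3 links review frequency to accrual and event rates without naming a target. The 125 and 175 are derived figures, not planned ones.

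**Conclusion.** The point holds. The control column in both tables is at I = 0.005 while the text fixes I = 0.007; this rests only on the protocol's formula and λ3. At the stated 90% power, mortality and group size in the same rows rest on different incidences. At year 3 the consequence is 79% against 91% power for 16,000 per group, or about 21,900 against 15,600 required. Those figures assume a standard two-proportion comparison and the printed relative risk.

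For the study columns the claim is weaker. Table 2's is close to a three-screen version of the model at 0.005 (0.94 to 15.06 against a printed 1.0 to 15.2), but the protocol gives no formula for that design. Table 1's departs from the model at years 2 and 3 even at 0.005.

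If Table 1's study column is recomputed as well, 16,000 per group gives about 67% (I = 0.005) or 81% (I = 0.007) power at year 3, and about 73% or 86% at year 4. The smallest group size then falls at year 4 (about 25,200 or 17,900) rather than year 3. These lower figures reflect both errors and should not be attributed to the incidence mismatch.

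**What to change.** State one planning incidence in section 15.2 and recompute the control, study and group-size columns of both tables from it. If 0.007 is the planning value, print the rates it produces. If 0.005 is meant as a cautious value, say so in the text and resize accordingly. Then restate the power of 16,000 per group at the chosen analysis time, preferably with expected deaths per arm.

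In the same pass, correct the I_r formula and either reproduce the year-2 and year-3 study values in Table 1 or explain them.

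The incidence correction costs only text and table edits. If the recomputed study column is adopted, power at 16,000 falls below 90% at either incidence, and the group size or analysis time would have to be reconsidered. The protocol places that decision before the main trial starts, since section 15.4 already allows its protocol to be revised after the pilot.
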